### 3.2 Accelerator

Physicians will treat with a stereotactic radiosurgery system using 6MV photons to deliver stereotactic body radiotherapy.

### 3.3 Doses

In this protocol, the linear quadratic formula is used to calculate equivalent doses. Three assumptions are made: 1) sublethal damage is completely repaired between fractions, 2) no repair of sublethal damage occurs during a given fraction, and 3) no repopulation occurs during the treatment course (i.e., there is no time factor). Equivalent dose at a specified dose/fraction  $d$ , for an assumed  $\alpha/\beta$  ratio  $r$ , is expressed as  $EQD_d$  ( $\alpha/\beta=r$ ). See table 2 for 2Gy/fraction equivalent doses. The 5-year bDFS outcomes for HDR series and for hypofractionated EBRT are superior to those reported using conventionally fractionated 3D conformal or IMRT (see table 1). This suggests that an  $EQD_2$  of 80 Gy or more may be required to achieve 5-year bDFS in the 96-98% range. At Stanford and Naples Community Hospital, toxicity following CyberKnife (7.25 Gy x 5 fractions, and 7 Gy x 5 fractions, respectively, both calculated 3-5mm from the prostate border) was minimal. In the Naples series, median PSA outcomes 1 year after treatment was 1.2ng/dL, somewhat greater than that reported in brachytherapy series. The protocol gave an  $EQ_2$  74.3 to 90.6Gy (for  $\alpha/\beta$  ratios of 3Gy and 1.5Gy, respectively); PSA response was excellent, falling to an average of 0.22ng/ml at 18 months. This protocol thus uses the Stanford dose and PTV: 7.25Gy x 5 fractions prescribed to the PTV, defined as the prostate expanded 3mm posteriorly, and 5mm elsewhere. The rapid dose gradient achievable with SBRT allows the simultaneous delivery of a greater dose to the prostate (GTV). To deliver a BED approaching that prescribed in the HDR monotherapy series, 8Gy x 5 is prescribed to the prostate. Thus the PTV receives an  $EQD_2$  of 74.3Gy (if  $\alpha/\beta=3$ ), or an  $EQD_2$  of 90.6Gy ( $\alpha/\beta=1.5$ ). The prostate receives an  $EQD_2$  ( $\alpha/\beta=3$ ) of 88Gy, or 108.6Gy for  $\alpha/\beta=1.5$ .

$$nd \times (1 + d/\square \square (\alpha/\beta))$$

where  $n$  is the # of fractions and  $d$  is the dose/fraction. The “alpha-beta ratio” characterizes the radiation response of a particular tissue; a higher value is indicative of a tissue that responds acutely to the effects of radiation. Due to their highly proliferative nature, most tumors fall into this category.

SBRT treatment will be given on non-consecutive days, excluding weekends. The prescription dose will be prescribed to the isodose line best encompassing the planning target volume (PTV) depending on the volume of tumor.

Institution/protocol	Dose/fx	#fxs	Total dose	2Gy/fx Equivalent Dose			
				Assuming $\alpha/\beta$ ratio of:	1.5Gy	3Gy	10Gy
Naples CyberKnife	7	5	35		85	70	49.6
Stanford CyberKnife	7.25	5	36.25		90.6	74.3	52.1
Beaumont HDR*	9.5	4	38		119.4	95	61.8
Demanes HDR*	7.25	6	43.5		108.8	89.2	62.5
This protocol: GTV	8	5	40		108.6	88	60
RTOG 0415	2.5	28	70		80	77	72.9

\*Does not account for heterogeneity in HDR plans.

### *3.4 Localization, Simulation and Treatment Planning*

#### **3.4.1 FIDUCIAL PLACEMENT:**

All patients will have gold fiducial seeds measuring 3-5 mm placed in the prostate prior to treatment planning. At least four fiducial seeds will be placed under transrectal ultrasound guidance, using either transperineal or transrectal approach, with local anesthesia and/or sedation as required. The physician will place seeds such that they are visible (and not superimposed) on orthogonal imaging, are not collinear, and ideally are separated by 2cm or more. Fiducials will be placed as an outpatient procedure; at least three seeds must be usable for tracking during treatment. If an interim analysis shows unacceptable fiducial migration with a specific technique or type of fiducial, further use of this technique or type of fiducial may be prohibited by the Principal Investigator. The side effects of implantation will be similar to a biopsy of the prostate. These include but are not limited to infection, bleeding, pain at local area, and dislocation of the marker. Alternatively, cone beam computed tomography (CBCT) can be used in lieu of fiducial markers at the discretion of the investigator.

#### **3.4.2 TREATMENT PLANNING IMAGING:**

To allow fiducial stabilization and resolution of swelling, planning studies will be imaged 5-10 days after fiducial placement. Alpha Cradle or a similar immobilization device will be used as needed. To avoid prostate distortion, in the primary CT used for treatment planning, no indwelling catheter shall be placed. If required to visualize the urethra, a catheter may be placed for the secondary imaging study only. All patients will be asked to empty their bladders prior to the CT to help promote a reproducible prostate position. CT scans will be taken for treatment planning. IV contrast will be given to all patients except those with an allergy or chronic renal insufficiency. CT slices will be 1 – 1.5mm, with 200-300 slices taken centered approximately at the prostate. The imaging sets will be downloaded to the appropriate treatment planning system to develop the radiosurgery treatment plan.

If not medically contraindicated, all patients will undergo MRI imaging to determine the anatomical borders of the prostate, and if possible, the urethra. This study will be fused to the treatment planning CT. No endorectal coil is allowed.

**3.4.2.1 URETHRAL IDENTIFICATION:** To record DVH data for the prostatic and membranous urethra, visualization of these structures is recommended, but not mandatory. If the urethra cannot be visualized and contoured, then to insure the prostatic urethra meets the dose constraint specified in 8.3.4.7, the prescription dose of 36.25Gy shall be no less than 75% of Dmax. To identify the urethra, the following may be employed:

MRI, if urethra can be identified. To verify that the MRI is capable of visualizing the urethra, on the first 3 cases an additional *secondary* scan (either MRI or CT) shall be performed with an indwelling catheter in place. This will be correlated with the MRI scan performed without a catheter; if the urethra can be reliably imaged, then subsequent catheter placement is not required.

A *secondary* CT or MRI scan with an indwelling urethral catheter in place. Urethrogram with contrast delineating the membranous and prostatic urethra.

Prior to treatment planning imaging, the patient will follow the bowel/urinary preparation procedures used for treatment. This will include emptying the bladder voluntarily or by catheterization if necessary. If the patient has moved his bowels in the past 72 hours no specific procedure is necessary. If he has been constipated without a bowel movement for greater than 72 hours an enema will be given. These measures are taken to help limit prostate motion and create a reproducible position from planning to treatment.

### *3.5 Treatment Delivery*

The planning data containing the coordinates of tumor isocenter, the external infrared markers, and the implanted markers are transferred to the appropriate platform depending on the treating machine. The daily initial positioning during treatment delivery will be performed using lasers and skin marks and infrared optical markers as appropriate. The target isocenter will be verified using daily imaging. Depending on the platform used, the moving target will be positioned within the beam under infrared and/or image guidance. If at any time a patient needs IV fluids for dehydration for diarrhea, we will cancel the next scheduled fraction and resume treatment on the following fraction if the diarrhea has improved.

### *3.6 Supportive Care*

#### *3.6.1 Diarrhea*

Patients will be instructed to begin taking loperamide after the first poorly formed or loose stool or first episode of 2 or more bowel movements in one day.

Loperamide should be taken in the following manner: 4 mg at the first onset of diarrhea, then, 2 mg after every episode of diarrhea until reaching the daily maximum dose.

Loperamide should not be taken prophylactically

Patients must notify the research team as to when they initiated loperamide therapy. If diarrhea persists despite loperamide therapy, then the patient should be evaluated for the need for IV fluid & electrolyte replacement.

Alternative medications

Somatostatin analog (Octreotide) 100 - 500 mcg SC/IV tid; maximum daily dose = 1500 mcg/day; alternatively, somatostatin analog may be given at 25-50 mcg/hour as a continuous IV infusion.

Atropine/diphenoxylate which is available as either a 0.025/2.5 tab, or 0.025/2.5 per 5 mL liquid. Patients should take 1-2 tabs PO tid or qid or 5-10 mL PO tid/qid.

Atropine/difenoxin (Motofen) 0.025/1 tab; 2 tabs PO x 1, then 1 tab PO q 2-4 hr (max 8 tabs per day)

Paregoric: (an antidiarrheal opiate): 5 - 10 mL ORALLY 1-4 times daily: maximum 40 mL/day

OTC meds: bismuth subsalicylate 262 mg tabs: 2 tabs PO q 1 hr prn; maximum 4200 mg/24 hr

#### **4.0 Patient Selection and Eligibility**

All of the following will be completed prior to enrollment in the study.

- 4.1 Evaluations Required for Eligibility:
  - 4.1.2 Complete history & physical examination including a digital rectal exam
  - 4.1.3 Assessment of performance status
  - 4.1.4 Pathologic confirmation of adenocarcinoma of the prostate
  - 4.1.5 Serum PSA, < 60 days prior to registration, or < 60 days prior to hormone therapy
  - 4.1.6 CBC, platelets, serum BUN and creatinine
  - 4.1.7 Ultrasound of prostate, or CT of pelvis to determine prostate size: volume =  $\pi/6 \times \text{length} \times \text{height} \times \text{width}$
  - 4.1.8 Measurement from CT or ultrasound  $\leq$  90 days prior to registration, or  $\leq$  14 days prior to registration if hormone therapy given
- 4.2 Patient questionnaires (see appendix VI).
  - 4.2.1 FACT-G questionnaire

- 4.2.2 AUA questionnaire
- 4.2.3 EPIC-26 questionnaire
- 4.2.4 SHIM questionnaire
- 4.2.5 Utilization of Sexual Medications/Devices questionnaire

#### 4.3 Patient Eligibility

All patients must meet the following criteria to be considered eligible for enrollment.

- 1. Histologically proven prostate adenocarcinoma
  - 1a. Gleason score 2-7
  - 1b. Biopsy within one year of date of registration
- 2. Clinical stage T1b-T2b, N0-Nx, M0-Mx (AJCC 6th Edition)
  - 2a. T-stage and N-stage determined by physical exam and available imaging studies (ultrasound, CT, and/or MRI)
  - 2b. M-stage determined by physical exam, CT or MRI. Bone scan not required unless clinical findings suggest possible osseous metastases.
- 3. PSA  $\leq$  20 ng/dL
- 4. Patients belonging in one of the following risk groups:
  - 4a. Low: CS T1b-T2a and Gleason 2-6 and PSA  $\leq$  10, or
  - 4b. Intermediate: CS T2b and Gleason 2-6 and PSA  $\leq$  10, or CS T1b-T2b, and Gleason 2-6 and PSA  $\leq$  20 ng/dL, or Gleason 7 and PSA  $\leq$  10 ng/dL
- 5. Prostate volume:  $\leq$  100 cc
  - 5a. Determined using: volume =  $\pi/6 \times$  length  $\times$  height  $\times$  width
  - 5b. Measurement from CT or ultrasound  $\leq$  90 days prior to registration.
- 6. ECOG performance status 0-1
- 7. No prior prostatectomy or cryotherapy of the prostate
- 8. No prior radiotherapy to the prostate or lower pelvis
- 9. No implanted hardware or other material that would prohibit appropriate treatment planning or treatment delivery, in the investigator's opinion.
- 10. No chemotherapy for a malignancy in the last 5 years.
- 11. No history of an invasive malignancy (other than this prostate cancer, or basal or squamous skin cancers) in the last 5 years.
- 12. No hormone ablation for two months prior to enrollment, or during treatment.
- 13. Completion of patient questionnaires in section 4.7.
- 14. Life expectancy of  $\geq$  10 years as determined by treating physician.
- 15. Consent signed.

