## 2.0 Objective

### PRIMARY OBJECTIVES:

- 2.1 The primary safety goal of this study is to determine, in both low-risk and intermediate-risk cohorts, the rates of acute and late grade 3-5 gastrointestinal and genitourinary toxicity observed during the initial 24 months following hypofractionated SBRT for prostate cancer. Patients will be followed for at least 5 years but possibly as long as 10 years, but initially we will strive to obtain 2 year follow-up results.
- 2.2 The primary efficacy goal is to document the rate of biochemical Disease-Free Survival (bDFS), Phoenix and ASTRO definitions, at 2 years. As above, we will ultimately aim for at least 5 years of follow-up but possibly as long as 10 years, with a short term goal of 2 years.

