#### 5.0 Treatment Administration and Evaluation

##### 5.1.1 EVALUATED STRUCTURES:

5.1.1.1 GTV: The Gross Tumor Volume (GTV) shall include the prostate; no more than 0.5cm of the immediately adjacent SV shall be included.

5.1.1.2 CTV: The Clinical Treatment Volume (CTV) shall include:

5.1.1.2.1 LOW-RISK PATIENTS: (CS T1b-T2a, PSA  $\leq$  10, Gleason score  $\leq$  6). Pathologic data from William Beaumont Hospital showed only 1% of low-risk patients had seminal vesicle (SV) involvement; this eliminates the need to treat SVs in this group. Thus the CTV shall equal the GTV.

5.1.1.2.2 INTERMEDIATE RISK PATIENTS: The Beaumont study also showed only 2% of “high-risk” patients (PSA  $>$  10, Gleason  $>$  6, and/or CS  $>$  T2a) had SV involvement distal to 2 cm from the prostate. The intermediate risk group CTV shall therefore be the GTV plus the proximal 2cm of SVs.

5.1.1.3 PTV: The prescription dose shall be delivered to the Planning Tumor Volume (PTV). While the static targeting accuracy of the radiosurgery machines are about 1mm^69, deformation of the prostate, and target movement occurring after imaging but before dose delivery could contribute to targeting uncertainty. Although the cumulative targeting uncertainty has not been accurately quantified, the 3-5mm GTV to PTV expansion employed in the Stanford series appears more than adequate. Stanford phase I data showed safely and early clinical response rates are acceptable with this PTV. Thus the PTV shall equal the CTV expanded 3mm posteriorly, and 5mm in all other dimension.

5.1.1.4 Microscopic evaluation of prostatectomy specimens may demonstrate EXTRACAPSULAR EXTENSION: 99% of microscopic extra prostatic disease should be within 3- 5mm of the prostate. Since 7.25Gy is prescribed 3-5mm outside the prostate, a dose adequate to address microscopic disease ( $\geq$ 6Gy x 5) will easily be delivered at 5mm.

5.1.1.5 NORMAL TISSUES: CONTOURING REQUIRED: The structures listed below will be contoured and evaluated with DVH analysis. Bowel peristalsis and bladder filling change the size and location of normal structures. If the CT and MRI (or secondary CT) show normal tissues in different locations immediately adjacent (i.e., within  $<$  2cm) the prostate, the contoured structure shall be a larger composite of both image sets. Grid size should be sufficiently large to include the entire structure.

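### The written intermediate-risk definition includes every low-risk patient, so the two cohorts in the primary safety objective overlap and have no unique denominators

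*Combined protocol and SAP*

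**What the plan says.** Section 4.3, criterion 4 requires "Patients belonging in one of the following risk groups" and lists two:

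- 4a begins "Low: CS T1b-T2a and Gleason 2-6 and PSA" and sets an upper PSA limit of 10.
- 4b has three limbs. The first, "Intermediate: CS T2b and Gleason 2-6 and PSA", has an upper limit of 10. The second, "or CS T1b-T2b, and Gleason 2-6 and PSA", has an upper limit of 20. The third, "or Gleason 7 and PSA", has an upper limit of 10.

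Neither 4a nor 4b says which group takes precedence when a patient meets both.

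Risk group is used in two places. Section 2.1 states the primary safety goal as grade 3-5 GI and GU toxicity rates "in both low-risk and intermediate-risk cohorts"; the Protocol Summary and 7.3 say the same in terms of grade 3 or higher. Section 5.1.1.2 sets the clinical target volume by group. For low risk it repeats the low-risk criteria and concludes "Thus the CTV shall equal the GTV". For the other group it says "The intermediate risk group CTV shall therefore be the GTV plus the proximal 2cm of SVs".

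**The concern.** Two cohorts that are reported separately should divide the patients between them. Here the second limb of 4b has only an upper PSA limit, so it takes in the men that 4a describes. A patient with T1c disease, Gleason 6 and a PSA of 6 meets 4a and also meets 4b.

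What is at stake is the per-cohort part of the primary safety objective. Two analysts working from the same data and the same text could put different numbers of patients in the denominators. On the literal reading the intermediate-risk cohort is the whole trial, and its toxicity rate is simply the overall rate. Because 5.1.1.2 attaches a target volume to each group, the definitions also need to agree there.

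**Working it through.** The plan gives no figure to reproduce; this is a check of set logic.

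**Inputs** (4.3, criteria 1 to 4)

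- Low (4a): T1b-T2a, Gleason 2-6, PSA ≤ 10.
- Intermediate limb 1: T2b, Gleason 2-6, PSA ≤ 10.
- Intermediate limb 2: T1b-T2b, Gleason 2-6, PSA ≤ 20.
- Intermediate limb 3: Gleason 7, PSA ≤ 10 (stage T1b-T2b through criterion 2).

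**Step 1, containment.** T1b-T2a lies within T1b-T2b, the Gleason ranges are equal, and PSA ≤ 10 lies within PSA ≤ 20. So 4a is a subset of limb 2. It does not meet limb 1 (different stage) or limb 3 (different Gleason score), so limb 2 alone causes the overlap.

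**Step 2, redundancy.** T2b lies within T1b-T2b and PSA ≤ 10 within PSA ≤ 20, so limb 1 is a subset of limb 2 and adds no one.

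**Step 3, enumeration.** Take four stages (T1b, T1c, T2a, T2b), Gleason 2 to 7, and PSA from 0 to 20 in steps of 0.5. Cells are combinations of characteristics, not patients.

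- 4a: 3 stages × 5 Gleason scores × 21 PSA values = 315 cells.
- Limb 2: 4 × 5 × 41 = 820 cells.
- Limb 3: 4 × 1 × 21 = 84 cells.
- Limb 1: 1 × 5 × 21 = 105 cells, all inside limb 2.
- 4b: 820 + 84 = 904 cells. Adding 4a adds none, so the eligible set is also 904.

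All 315 of 315 low-risk cells meet 4b, and 4b is 904 of 904 eligible cells.

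**Step 4, what exclusivity would change.** Purely as arithmetic, and not as a recommended rule, let limb 2 start above PSA 10. It then has 4 × 5 × 20 = 400 cells, and 4b has 400 + 105 + 84 = 589. The overlap falls from 315 to 0, and 589 + 315 = 904, so eligibility is unchanged. Limb 1 then does separate work.

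**Step 5, size in patients.** The documents give no risk mix. For assumed low-risk shares of the planned 200:

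- 25%: 50 meet both definitions; the intermediate cohort is 200 literally, 150 if exclusive.
- 50%: 100 meet both; 200 literally, 100 if exclusive.
- 75%: 150 meet both; 200 literally, 50 if exclusive.

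**Step 6, PSA unit.** Criterion 3 of 4.3 sets the limit at 20 ng/dL, and 4b uses the same unit; 6.4.1.1 defines failure in ng/ml. One dL is 100 ml, so 20 ng/dL is 20 / 100 = 0.2 ng/ml: a 100-fold difference if read literally.

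**The case against.** The strongest reply is that exclusive groups were plainly intended. Criterion 4 speaks of membership in one group and lists low risk first. Section 5.1.1.2.1 does not depend on 4.3: it restates the low-risk criteria beside their own target volume. Section 5.1.1.2.2 quotes a contrast group from the cited pathology study (PSA above 10, Gleason above 6, and/or stage above T2a). Among eligible patients, that group is exactly everyone who does not meet 4a. A careful reader would probably classify low risk first.

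Much of this stands as evidence of intent, but it does not supply a rule. No section states precedence. The contrast group describes the cited study's patients, whom that section calls high-risk, and 5.1.1.2 never defines this trial's intermediate-risk group.

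It is also right that no primary decision changes. The limits U and L in 7.3.1 use the total number of patients, 7.2.3 sets 200 in total with no number per group, and the stopping rule in 7.4 is pooled.

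Three stronger inferences are tempting and should be resisted:

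- A reader might say the low-risk cohort could be anything from all such men to none. The empty cohort is a logical extreme: it would leave 5.1.1.2.1 applying to nobody and an objective that names both cohorts impossible to report.
- A reader might extend the problem to bDFS. The words about both cohorts attach only to toxicity. The bDFS objective covers low and intermediate risk together, and although 7.2.2 derives the 92% criterion from low-risk series, L is applied to all patients.
- A reader might take the redundant limb as proof that a bound was dropped. It suggests so, but redundant drafting would look the same.

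**Conclusion.** The classification rule is wrong as written. Every patient who meets 4a also meets 4b, and 4b covers the entire eligible set. The cohort-specific toxicity rates in the primary safety objective therefore lack unique denominators. This rests on the text alone; the 50 to 150 patients with dual membership depend on the assumed 25% to 75% low-risk share of 200.

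The effect is confined to cohort reporting and to the match between 4.3 and 5.1.1.2. It does not reach eligibility, sample size, power, U, L or the stopping rule. Nor do the documents support saying that target volumes were left without guidance, since 5.1.1.2.1 addresses men with low-risk features directly. What remains there is an inconsistency between sections.

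The PSA unit is a separate discrepancy in an eligibility threshold and adds no weight to the overlap. The correction should be made, but no primary decision depends on it.

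**What to change.** State one mutually exclusive risk-group classification for cohort reporting, so that each patient counts in exactly one cohort, and have 4.3 and 5.1.1.2 both refer to it. The sponsor must reconcile those two sections on which group each patient belongs to for the target volume; this review takes no position on which target-volume rule is right. In the same edit, reconcile the PSA unit between 4.3 and 6.4.1.1.

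The cost is a short text correction. Stage, Gleason score and PSA are already collected for eligibility, so no new data are needed, and making the groups exclusive within the eligible set leaves the sample size and the pooled analyses as they are.

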#### 5.0 Treatment Administration and Evaluation

##### 5.1.1 EVALUATED STRUCTURES:

5.1.1.1 GTV: The Gross Tumor Volume (GTV) shall include the prostate; no more than 0.5cm of the immediately adjacent SV shall be included.

5.1.1.2 CTV: The Clinical Treatment Volume (CTV) shall include:

5.1.1.2.1 LOW-RISK PATIENTS: (CS T1b-T2a, PSA  $\leq$  10, Gleason score  $\leq$  6). Pathologic data from William Beaumont Hospital showed only 1% of low-risk patients had seminal vesicle (SV) involvement; this eliminates the need to treat SVs in this group. Thus the CTV shall equal the GTV.

5.1.1.2.2 INTERMEDIATE RISK PATIENTS: The Beaumont study also showed only 2% of “high-risk” patients (PSA  $>$  10, Gleason  $>$  6, and/or CS  $>$  T2a) had SV involvement distal to 2 cm from the prostate. The intermediate risk group CTV shall therefore be the GTV plus the proximal 2cm of SVs.

5.1.1.3 PTV: The prescription dose shall be delivered to the Planning Tumor Volume (PTV). While the static targeting accuracy of the radiosurgery machines are about 1mm^69, deformation of the prostate, and target movement occurring after imaging but before dose delivery could contribute to targeting uncertainty. Although the cumulative targeting uncertainty has not been accurately quantified, the 3-5mm GTV to PTV expansion employed in the Stanford series appears more than adequate. Stanford phase I data showed safely and early clinical response rates are acceptable with this PTV. Thus the PTV shall equal the CTV expanded 3mm posteriorly, and 5mm in all other dimension.

5.1.1.4 Microscopic evaluation of prostatectomy specimens may demonstrate EXTRACAPSULAR EXTENSION: 99% of microscopic extra prostatic disease should be within 3- 5mm of the prostate. Since 7.25Gy is prescribed 3-5mm outside the prostate, a dose adequate to address microscopic disease ( $\geq$ 6Gy x 5) will easily be delivered at 5mm.

5.1.1.5 NORMAL TISSUES: CONTOURING REQUIRED: The structures listed below will be contoured and evaluated with DVH analysis. Bowel peristalsis and bladder filling change the size and location of normal structures. If the CT and MRI (or secondary CT) show normal tissues in different locations immediately adjacent (i.e., within  $<$  2cm) the prostate, the contoured structure shall be a larger composite of both image sets. Grid size should be sufficiently large to include the entire structure.

5.1.1.5.1 RECTUM: defined as a solid structure, including the lumen and rectal wall, extending from the level of the ischial tuberosity to the sigmoid flexure.

5.1.1.5.2 BLADDER, defined as a solid structure including the bladder wall and lumen.

5.1.1.5.3 PENILE BULB: the portion of the bulbous spongiosum that lies inferior to the urogenital diaphragm.

5.1.1.5.4 SIGMOID COLON OR OTHER BOWEL lying within 2 cm of the PTV should be contoured.

5.1.1.6 NORMAL TISSUES: COUNTOURING REQUIRED IF VISUALIZED:

5.1.1.6.1 PROSTATIC URETHRA, defined as the lumen-mucosal interface, extending from bladder neck to the membranous urethra. If visible on planning studies, this shall be contoured and evaluated. If not visible, then contouring is not required, however the prescription dose (36.25Gy) should be prescribed at 75% of Dmax or greater.

5.1.1.6.2 MEMBRANOUS URETHRA shall be contoured, if visible.

5.1.1.6.3 NEUROVASCULAR BUNDLE, if visible on MRI or CT: should be contoured in transverse planes extending from the prostatic apex to the base.

5.1.2 DOSE SPECIFICATIONS: All specified doses are for the entire treatment course.

5.1.2.1 The **PRESCRIPTION DOSE** of **36.25Gy** shall be the dose to the **PTV**:

5.1.2.1.1 *Per protocol*: V36.25Gy shall be at least 95%, and the prescribed dose shall be 65-85% of Dmax (or 75-85% if urethra not contoured).

5.1.2.2 A **SECONDARY DOSE** of **40Gy** shall be the dose to the **GTV**:

5.1.2.2.1 *Per protocol*: GTV V40Gy shall be at least 95%.

5.1.2.2.2 GTV+1mm shall also be contoured for DVH analysis.

**Table 3.** Normal Tissue Dose Constraints for RTOG 0126, and the BEDs for Acute and Late Effects

RTOG 0126		Constraint	Acute effects: $\alpha/\beta = 10$		Late effects: $\alpha/\beta = 3$	
			BED	5 fx equiv	BED	5 fx equiv
Bladder	D15	80Gy	94.4	48.7	128	37.8
	D25	75Gy	88.5	46.6	120	36.4
	D50	65Gy	76.7	42.3	104	33.5
Rectum	D15	75Gy	88.5	46.6	120	36.4
	D25	70Gy	82.6	44.5	112	35.0
	D50	60Gy	70.8	40.0	96	31.9
Penile bulb	median	52.5Gy	62.0	36.4	84	29.5

